### **12.3. Figures and listings of Pharmacodynamic parameters**

In addition, a plot will be presented showing the mean concentration and Standard Error (SE) of the CRP and ESR up to Week 24 for the pharmacodynamic population and up to Week 48 for the pharmacodynamic – 2nd treatment course in Main Study Period Subset by treatment group (CT-P10 group vs. Reference products group). A plot will also be presented for the median of the B-cell counts at each visit and time point up to Week 24 for the PD population and up to Week 48 for the pharmacodynamic – 2nd treatment course in Main Study Period Subset by treatment group (CT-P10 group vs. Reference products group).

All pharmacodynamic data for CRP, ESR, anti-CCP and RF will be listed for the pharmacodynamic population by treatment group and visit. Anti-CCP and RF categories for the PD population will also be listed by treatment group, visit and time point. A listing will be produced for the PD population displaying B-cell counts, log-transformed B-cell counts, and AUC by treatment group, visit, and time point.

### 13. Safety Analyses

The safety analyses will be performed on the safety population and safety – Extension Study Period subset by treatment group presenting data on hypersensitivity monitoring via vital sign measurements (including blood pressure, heart and respiratory rates, and temperature) and electrocardiograms (ECG), immunogenicity tests, vital sign measurements, ECGs, signs and symptoms of tuberculosis (TB), physical examination findings, adverse events (AEs), infections, Infusion-Related Reactions (IRRs), malignancy, clinical laboratory results (hematology, clinical chemistry, urinalysis, and immunoglobulins), and pregnancy tests. Combined PTs using the [APPENDIX 3: Rule of combining Preferred Terms](#) will be summarized in AE tables. Listings will include the PTs as coded without applying the PT combining rule.

#### 13.1. Adverse Events

An AE is defined as any untoward medical occurrence in a patient enrolled (i.e., when the informed consent form (ICF) is signed) into this study regardless of its causal relationship to study drug.

The Medical Dictionary for Regulatory Activities (MedDRA) version 18.1 or higher will be used to code all AEs. AEs will be graded for intensity according to the Common Terminology Criteria for Adverse Events (CTCAE) v4.0.

Listings for AEs will include the following information: SOC, PT and verbatim term; start and stop date; frequency (intermittent, continuous); outcome (recovered/resolved, recovering/resolving, recovered/resolved with sequelae, not recovered/not resolved, fatal, unknown); any treatment required (no, yes with specified treatment); intensity (Grade 1 to 5); action taken by investigator (dose increased, dose decreased, no action taken, permanently discontinued, stopped temporarily, dose delay); relationship to study drug (unrelated, possible, probable, definite); whether the event was serious (no, yes); and whether subject was terminated from the study due to the AE. All adverse events will be listed.

In summaries, adverse events will be considered to be related if the relationship is possible, probable, or definite. AEs with no relationship recorded will be summarized separately under a missing category.

If the data of an AE is partial or missing, the following rules will be applied.

- If the day of an Adverse Event is missing (e.g. XXFEB2016), the month and year of the partial date will be compared to the date of the first exposure to study drug.
  - If the month and year are equal for both dates, the AE start date will be imputed as the earlier date of: (i) the date of the first exposure to study drug, and (ii) the recorded end date of the AE.
  - If the month and year are not equal, the AE start date will be imputed as the first day of the month (e.g. 01FEB2016).

- If the day and month is missing (e.g. XXXXX2016), the year of the partial date will be compared to the date of the first exposure to study drug.
  - If the years of both dates are equal, start date will be imputed as the earlier date of: (i) the date of the first exposure to study drug, and (ii) the recorded end date of the AE.
  - If the year is not equal, start date will be imputed as the 1st of January of the partial date year (e.g. 01JAN2016).

If the AE start date is missing (e.g. XXXXXXXXX), start date will be imputed as the earlier date of: (i) the date of the first exposure to study drug, and (ii) the recorded end date of the AE.

A treatment-emergent AE (TEAE) is defined as any event not present before exposure to study drug or any event already present that worsens in either intensity or frequency after exposure to study drug.

TEAEs will be summarized by relationship, intensity, SOC and PT for the safety population and safety – Extension Study Period subset, displaying the number and percentage of patients with at least one TEAE using only the most severe TEAE recorded at each level of summarization. The total number of events and number of patients with at least one TEAE will also be displayed. Although PML is an AE of special interest, it is captured only by a PT ‘Progressive multifocal leukoencephalopathy’. Therefore, do not generate an additional table for PML and it will be summarized with TEAEs.

The following tables will be presented by treatment group:

- TEAE by intensity
- Treatment-Emergent SAE (TESAE) by intensity
- TESAE by serious criteria
- TEAE leading to permanent discontinuation of study drug by intensity
- TEAE classed as malignancy by intensity
- TEAE classed as infections by intensity
- TEAE due to infusion-related reaction by intensity
- Proportion of patients with at least one TEAE due to infusion-related reaction by ADA status

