##### **5.4.5.2. Safety – Extension Study Period Subset**

The safety population – Extension Study Period subset will consist of all patients in the safety population who have received at least one (full or partial) dose of study drug during the Extension Study Period.

The safety population – Extension Study Period subset will be the primary population subset for the summary of Extension Study Period safety data.

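### SAP 13.1 has no Extension anchor for partial AE start dates or for treatment emergence, so missing-day AEs in the switch month are dated before the switch and the content of the Extension AE tables is undefined

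*SAP*

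**What the plan says.** SAP 13.1 gives one set of rules for incomplete AE start dates.

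- Day missing: "the month and year of the partial date will be compared to the date of the first exposure to study drug". If they match, the start is the earlier of first exposure and the recorded AE end date. If they do not, "If the month and year are not equal, the AE start date will be imputed as the first day of the month".
- Day and month missing: the year is compared with that of first exposure. If it matches, "start date will be imputed as the earlier date of: (i) the date of the first exposure to study drug" or the recorded end date. If it does not, the start is 1 January of the recorded year.
- Whole date missing: the earlier of first exposure and the recorded end date.

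The same section defines a TEAE as "any event not present before exposure to study drug or any event already present that worsens in either intensity or frequency" after exposure. It gives no separate definition for the Extension. It then plans the tables: "TEAEs will be summarized by relationship, intensity, SOC and PT for the safety population and safety – Extension Study Period subset".

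SAP 5.4.5.2 defines the Extension safety subset as those patients in the safety population who received any dose in the Extension, and says that this subset "will be the primary population subset for the summary of Extension Study Period safety data". SAP 5.7 shows Main Study Period results by product and Extension results by Groups 1 to 4 plus the combined switched group. Under SAP 4.1, Group 2 (from Rituxan) and Group 4 (from MabThera) change to CT-P10 at Extension Week 0, while Groups 1 and 3 stay on their product.

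**The concern.** At Week 0 the rule is cautious: an AE that could have begun before or after the infusion is put on the infusion date and counts as emergent, unless it is recorded as having ended earlier. At the Extension infusion the same text works the other way, because that infusion is not an anchor. An uncertain AE goes to the start of the month or year, which is almost always before the switch.

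SAP 4.1 gives additional safety and immunogenicity as the purpose of the Extension. For Groups 2 and 4 the onset date decides which product the patient was receiving. Separate Main and Extension displays require each AE to be assigned to a period, and the SAP does not say how.

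**Working it through.** **Inputs.** Imputation rules: SAP 13.1. Extension infusion between Week 48 and Week 52, that is Day 336 to Day 364: SAP 4.1. Subset definition: SAP 5.4.5.2. Uniform calendar dates are an assumption.

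**1. Reproduce the rule.** Coded as written, an AE recorded as XXFEB2016, with first exposure in another month, gives 01FEB2016, which is the SAP's own example.

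**2. Which branch applies at the switch?** Every first-infusion date in a four-year calendar was crossed with every switch day: 1,461 × 29 = 42,369 pairs. The switch shares month and year with first exposure in 0 of them. The first-of-month branch always applies.

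**3. How often is the imputed date before the switch?** Always, except for a switch on the 1st. The run gives 96.7%. By hand: 1 − 12/365.25 = 0.967.

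**4. How many switch-month events would be wrongly placed?** For a month of L days, averaged over switch days:

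- Share of days on or after the switch: (L + 1)/(2L). For L = 30, 31/60 = 0.517. The run over real months gives 51.6%.
- Of those, the share imputed to before the switch: (L − 1)/(L + 1). For L = 30, 29/31 = 0.935. The run gives 93.6%.

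The remaining switch-month days, about 48%, precede the switch, and events on them are placed on the correct side.

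**5. Only the year known, equal to the switch year.** The date becomes 1 January, or first exposure if both fall in the same year. It precedes the switch in 99.7% of pairs (1 − 1/365.25 = 0.997; the exception is a switch on 1 January).

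**6. Whole date missing.** The imputed date is never later than first exposure.

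**Example.** First infusion 20 May 2015; Day 336 is 20 April 2016. An AE recorded as XXAPR2016 becomes 01APR2016, 19 days before the switch.

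**7. What happens to that AE in the tables?**

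| Reading of the Extension TEAE tables | Result |
|---|---|
| Only AEs with onset on or after the first Extension infusion (not written in the SAP) | The AE is left out; in Groups 2 and 4 it falls to the pre-switch product |
| All TEAEs of patients in the subset (the literal text) | The AE stays in, and so do all their Main Study Period TEAEs, under the Extension group labels |

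SAP 13.2 limits its table of grade 3 or higher laboratory results to data from the period concerned. SAP 13.1 has no matching sentence for AEs.

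**The case against.** The strongest reply is that nothing in the SAP removes these AEs. A reader might infer that they drop out of the Extension tables, but SAP 5.4.5.2 selects patients, not event dates. An AE dated to the 1st of the switch month still follows Week 0 exposure, so read literally it remains a TEAE in an included patient. That stands, and the loss is conditional on an onset filter. It does not rescue the plan, because the literal reading fills the switched columns with events from before the switch.

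A reader might also infer that the rule makes switching look safer. The documents do not show this. Group 3 is the randomized comparator for Group 2, and both it and Group 1 are misdated in the same way. A biased Group 2 versus Group 3 contrast is therefore not established.

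Nor is every partial date misplaced. Missing-day events that truly preceded the infusion land on the correct side. A year-only AE can be right too: with a switch in October 2016, an AE recorded only as 2017 goes to 1 January 2017, after the switch.

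Other provisions limit the effect. AEs are asked about at every visit (Protocol 6.5.10.2), onset is collected (Protocol 6.5.10.3), data discrepancies are resolved with sites (Protocol 7.9), and all AEs are listed with start and stop dates (SAP 13.1). Infusion-related reactions are flagged on the eCRF and summarised per treatment course (SAP 13.1.4.3), so they may not depend on an imputed date. The other AE tables, including infections, malignancy, SAEs and discontinuations, have no such provision.

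**Conclusion.** The point holds as a defect in a stated rule joined to a missing definition. The imputation is cautious at Week 0 and the reverse at the switch, and no rule assigns an AE to the Main or Extension period. Either reading gives an Extension AE table that does not describe the period after the switch.

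The percentages describe the rule under uniform calendar dates and Extension dosing on Day 336 to 364. They do not estimate lost events: the documents give no count of AEs with incomplete dates, so the effect may be small. The TEAE wording says exposure without the word first; first exposure is the natural reading, since every Extension patient was already exposed at Week 0. A reader might carry the point over to medication dates in SAP 9.1, which also use the first infusion, but no resulting harm is shown there.

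**What to change.** In SAP 13.1:

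1. Define an Extension TEAE as an AE with onset, or worsening in intensity or frequency, on or after the first Extension infusion. Tabulate only these for the Safety – Extension subset.
2. For patients in that subset, set the start to the earlier of the first Extension infusion date and the recorded AE end date in two cases: the day is missing and the month and year equal those of that infusion; or only the year is known, it equals the year of that infusion, and it differs from the year of first exposure.
3. Keep the present rule for fully missing dates, and list those AEs separately for Extension patients. Moving them all to the switch would be too blunt: with 48 weeks before and 24 after, and onset assumed evenly spread, 48/72 = 67% would truly precede it.

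The cost is a few sentences and one derivation. Some events that truly began before the switch will be counted after it, the same cautious convention that the SAP already uses at Week 0.

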#### **13.1.1. Death**

A listing will be provided showing any deaths during the study period in the safety population including detailed in [Section 13.1](#).

### **13.1.2. Serious Adverse Events**

An SAE is defined as any event that results in death, is immediately life threatening, requires inpatient hospitalization or prolongation of existing hospitalization, results in persistent or significant disability/incapacity, or is a congenital anomaly/birth defect. Important medical events that may not result in death, be life threatening, or require hospitalization may be considered an SAE when, based upon appropriate medical judgment, they may jeopardize the patient and may require medical or surgical intervention to prevent one of the outcomes listed in this definition.

TESAEs will be summarized by relationship, intensity, SOC, and PT for the safety population and safety – Extension Study Period subset, displaying the number and percentage of patients with at least one TESAE using only the most severe SAE recorded at each level of summarization. The total number of events and number of patients with at least one TESAE will also be displayed.

All SAEs will be listed including the variables detailed in [Section 13.1](#).

### **13.1.3. Treatment emergent Adverse Events leading to Permanent Study Drug Discontinuation**

TEAEs which lead to permanent discontinuation of the study drug will be summarized by relationship, intensity, SOC, and PT for the safety population and safety – Extension Study Period subset, displaying the number and percentage of patients with at least one TEAE leading to permanent discontinuation of the study drug, using only the most severe TEAE recorded at each level of summarization. The total number of events and number of patients with at least one TEAE which led to permanent discontinuation of the study drug will be also displayed.

All AEs leading to permanent discontinuation of study drug will be listed.

### **13.1.4. Treatment emergent Adverse Events of Special Interest**

Infection, malignancy and infusion-related reaction are considered TEAEs of special interest.

#### **13.1.4.1. Infections**

Infections are considered AEs of special interest and include but are not limited to serious, including fatal, bacterial including tuberculosis, fungal, and new or reactivated viral infections. New or reactivated viral infections include cytomegalovirus, herpes simplex virus, parvovirus B19, varicella zoster virus, West Nile virus, and hepatitis B and C. Infections are coded with a SOC of “Infections and infestations”.

Treatment-emergent infections will be summarized by relationship, intensity, SOC, and PT for the safety population and safety – Extension Study Period subset, displaying the number and percentage of patients with at least one TEAE using only the most severe TEAE recorded at each level of summarization. The total number of events and number of patients with at least one treatment-emergent infection will also be displayed.

#### **13.1.4.2. Malignancy**

TEAEs will be determined to be malignancy if they are coded with a PT of “cancer”, “carcinoma” or “lymphoma” in a SOC of “neoplasm, malignant and unspecified (including cyst and polyps)”.

Malignancy will be summarized for the safety population and safety – Extension Study Period subset, by relationship, intensity, SOC, and PT, displaying the number and percentage of patients with at least one TEAE using only the most severe TEAE recorded at each level of summarization. The total number of events and number of patients with at least one treatment-emergent malignancy will also be displayed.

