4.2.1 Reasons for Withdrawal

Reasons for withdrawal include the following:

- Patient develops signs of disease progression
- Patient experiences no efficacy from the study drug
- Patient withdraws consent or refuses to continue treatment or procedures/observations
- Patient develops any malignancy
- Patient has any AE that would compromise his or her safety if he or she continues to participate in the study
- Patient has a significant or major protocol violation
- Patient is lost to follow-up
- Patient dies
- Sponsor terminates the study

The investigator will also withdraw a patient upon the request of CELLTRION, Inc. Upon occurrence of a serious or intolerable AE, the principal investigator will confer with the sponsor. Any patient may withdraw his or her consent at any time. CELLTRION, Inc. or its designee may be contacted if clarification is required on a case-by-case basis.

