7.8.4.2 Adverse Events

Adverse events will be coded to system organ class (SOC) and preferred term (PT) according to MedDRA. Adverse events will be graded for severity according to the CTCAE v4.0.

The following AE summaries will be reported by SOC, PT, and treatment:

- Number and percentage of patients reporting at least 1 AE
- Number and percentage of patients reporting at least 1 SAE
- Number and percentage of patients discontinuing the study drug due to an AE
- Number and percentage of patients with AEs of special interest (infusion-related AEs and infections)

If more than 1 AE is recorded for a patient within any SOC or PT, the patient will be counted only once within the respective summary.

Adverse events will also be summarized by maximum intensity and relationship to study drug with the percentage of patients in each category. If more than 1 AE is recorded for a patient within any SOC or PT, the patient will only be counted once using the most severe assessment.

Adverse events of special interest will also be summarized by intensity.

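### SAP 13.1.4.2 identifies malignancy by three words in the preferred term, so melanoma, leukaemia, myeloma and sarcoma would be left out of the malignancy table

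*SAP*

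**What the plan says.** - **Status of the event.** SAP 13.1.4 states: "Infection, malignancy and infusion-related reaction are considered TEAEs of special interest". The protocol does not go that far. Its adverse event definitions (6.5.10.1) and its planned summaries (7.8.4.2) name only infusion-related events and infections as being of special interest.
- **The rule.** SAP 13.1.4.2: "TEAEs will be determined to be malignancy if they are coded with a PT of" one of three words (cancer, carcinoma, lymphoma), and the term must also sit in the neoplasm SOC.
- **The output it feeds.** The list of tables in SAP 13.1 includes "TEAE classed as malignancy by intensity". Section 13.1.4.2 describes it as counts and percentages by relationship, intensity, SOC and PT.
- **How the other two special-interest events are found.** Infections are taken as a whole SOC (SAP 13.1.4.1). Infusion-related reactions are flagged in the eCRF (SAP 13.1.4.3). Only malignancy depends on chosen words.

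**The concern.** The three words are not offered as examples; the sentence reads as the whole criterion. Several major classes of malignant tumour have names that contain none of them, so the table would be narrower than its title. Nothing in the output would tell a reader that these tumour types had been filtered out.

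The haematological gap deserves notice. The study drug acts by depleting B-cells, and protocol 4.1.2 excludes patients with a history of lymphoma or of lymphoproliferative disease, naming the two separately. The rule picks up the first and not leukaemia or myeloma.

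The SAP also leaves open whether a word must be part of the PT or all of it. Two programmers could therefore produce different tables from the same data.

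**Working it through.** The plan gives no figure to reproduce here. The check applies the rule as written, then looks for anything elsewhere that would repair it.

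**Step 1. Apply the rule.** Each term was tested against the three words in two ways: does it contain one of them, and is it identical to one of them?

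| Term | Contains one of the words | Identical to one of the words |
|---|---|---|
| melanoma | no | no |
| leukaemia | no | no |
| myeloma | no | no |
| sarcoma | no | no |
| breast cancer | yes | no |
| basal cell carcinoma | yes | no |
| lymphoma | yes | yes |

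The first four fail on either reading. On the whole-term reading, breast cancer and basal cell carcinoma fail as well.

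**Step 2. Look for a repair.**
- No section adds a standardised query, a term list, an eCRF flag or a medical review for malignancy.
- The Data Review Meeting in SAP 5.6 is described only as categorising protocol deviations.
- Appendix 3, which merges PTs for the adverse event tables, has no neoplasm rows.
- Taking the whole SOC, as is done for infections, would not work unchanged. Its name in 13.1.4.2 also covers unspecified growths, cysts and polyps. Some filter is needed; this one is too narrow.

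**Step 3. Trace an omitted event**, taking a melanoma as the example.
- *Overall TEAE tables* (SAP 13.1): included, under its own PT within the SOC, by treatment group.
- *Serious-event table and listing* (13.1.2): included if serious.
- *Discontinuation table and listing* (13.1.3): included if study drug is permanently stopped.
- *Listings* (13.1): included, since "All adverse events will be listed".
- *Malignancy table* (13.1.4.2): absent.

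**Step 4. Size.** The number of events missed would be the number of malignancies multiplied by the share whose PT lacks the three words. The documents give neither quantity. What can be shown is the effect of one missed case on a displayed percentage. Planned numbers (protocol 4.1 and 7.5) serve as denominators, on the assumption that the safety population is close to them:

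- CT-P10 or Rituxan: 1/149 = 0.67%
- MabThera: 1/63 = 1.59%
- Combined reference group: 1/212 = 0.47%

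**The case against.** The strongest reply is that no event is lost from the report. As traced above, a melanoma or leukaemia stays visible by arm under its own PT. The SAP accepts that route for another event: in 13.1 it gives progressive multifocal leukoencephalopathy no table of its own and leaves it to the TEAE table. The malignancy output is purely descriptive, with no test or confidence interval, and the protocol never named malignancy as an event of special interest. All of this stands and limits the consequence. It does not justify a table that undercounts its own subject. The leukoencephalopathy comparison is also incomplete: the SAP relies there on a single PT that identifies the event, whereas for malignancy it promises a separate summary.

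Three stronger readings are tempting, and the documents do not support them.

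- **That withdrawals for malignancy would be undercounted.** Protocol 4.2.1 lists "Patient develops any malignancy" as a reason for withdrawal, and SAP section 6 reports it as its own disposition category. That category does not use the PT rule, so it is unaffected. The two displays could disagree for the same patient, but only the malignancy table would be wrong.
- **That a percentage undercount can be stated.** Any such figure needs an assumed malignancy rate and then supposes that a case is in fact missed. The documents give no rate and no mix of tumour types. Protocol 4.1.2 also excludes recent malignancy, with stated exceptions, and any history of lymphoma or lymphoproliferative disease.
- **That the comparison between arms would change.** No inference is planned on malignancy, and the PT-level counts remain available to anyone comparing the arms. No primary or secondary hypothesis is touched.

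**Conclusion.** The rule is wrong as written. If it is followed exactly, malignant terms without the words cancer, carcinoma or lymphoma are left out of the malignancy table, and nothing else in the SAP brings them back. This rests on reading the sentence in 13.1.4.2 as the complete criterion, which is how it is worded; it does not depend on how the word match is programmed.

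The fault is one of definition in a single descriptive safety summary. It may turn out to affect no patient at all. The efficacy and pharmacokinetic conclusions, the general adverse event tables, the listings and the disposition counts are unaffected. It still merits correction, because a reader will take the table titled malignancy as the trial's count of malignancies.

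**What to change.** Before database lock and unblinding, replace the three-word rule in SAP 13.1.4.2 with one of the following, and use that definition for the malignancy table:

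1. the standard MedDRA malignancy query, with its version and scope stated; or
2. a complete list of the malignant PTs in the neoplasm SOC, confirmed by medical review blinded to treatment.

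SAP 5.3 allows some sponsor, biostatistics and medical writing staff to be unblinded for the Week 24 report, so the term list should be confirmed by people outside that group. Matching should be on whole PTs from the query or list, which also removes the ambiguity between partial and whole-term matching. A sentence should record that malignancy is of special interest under the SAP and was not so named in the protocol.

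The cost is one or two SAP sentences, one programming lookup and a short term review. No new data are needed.
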